9.2.3.2 Preliminary end of study

The following reasons may necessitate a preliminary termination of the whole trial

- Excessive number of non-responders or rapid relapses
- Excessive incidence of \geq III° toxicities CTACE, especially multiple V° toxicities
- New results from other studies or publications, making a continuation of this trial unreasonable or unethical

In the aforementioned cases, the lead investigators inform the Steering Committee of the ILROG, as constituted by international experts in the field of RT in lymphoma diseases, about the issue which has to decide on a study continuation within one month.

9.3 Data Monitoring Committee

A Data Monitoring Committee (DMC) will be established to provide the sponsor with recommendations regarding study modification, continuation or termination. (This includes the decision on how to proceed after contact with the Steering Committee of ILROG in case of severe adverse events.)

Procedures governing the convening and execution of the responsibilities of the DMC are specified:

The DMC is a group of radiooncological experts external to the Study Management in Muenster, assessing the progress, safety of data and, if needed critical efficacy endpoints of the study. The DMC may review unhidden study information during the conduct of the study. Based on its review the DMC can submit recommendations regarding study modification, continuation or termination.

A closed DMC meeting should be performed at half-time of the study (i.e. after the first year) or at the discretion of the study investigators. The documentation of a DMC meeting is kept in the study center in Muenster for 10 years.

10 Milestones

10.1 Study Duration

Planned recruitment duration: 1.5 years

Duration of single patient participation: between 6 months - 2 years

Planned overall duration of the study: 2 years

Planned start of data collection (first patient inclusion): September 01, 2019

Last patient inclusion: February 28, 2021

Planned end of data collection: (August 31, 2021). Under the impact of the COVID 19 pandemic the study period will be extended by 6 months until February 28 2022.

11 Statistical Considerations

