Participating Centers:	University Hospitals of: Beijing, Essen, Heidelberg, Kiel, Gießen-Marburg, Muenchen LMU, Muenchen TU, Muenster, New York MSKCC, Rochester, Singapore, Tokyo, Torino, Tuebingen, Boston, San Francisco, Toronto. Other expert hospitals: Bielefeld Franziskus Hospital, Mönchengladbach Kliniken Maria Hilf. Participating (Inter-) national centers after approval of their Ethics Committee/ Institutional Review Board.
Trial duration /Schedule:	Planned recruitment duration: 1.5 years Duration of single patient participation: RT intervention of two weeks plus 6 months after end of treatment Planned overall duration of the study: 2 years Planned start of recruiting/data collection: September 01, 2019 Planned end of data collection: (August 31, 2021) Under the impact of the COVID 19 pandemic the study period will be extended by 6 months until February 28 2022. Planned final report of study results: (August 31 2022) February 28 2023.
Visits:	Visits summary: Baseline visit, first day of RT treatment, second day (after 4 Gy), 5 th day of RT (after 10 Gy), last day of RT (after 20 Gy), 6 weeks after end of RT±5 d, 3 and 6 and 9 months after end of RT±3 weeks, 1 year after end of RT±3 weeks, 2 years after end of RT±3 weeks.
Financial Support:	An application for funding was submitted to the IZKF Muenster and to the DLH-foundation.

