3.2.2 Secondary Endpoints

-**Quality of life** (QoL) according to EORTC (QLQ C30 and STO22), at baseline visit/ after 20 Gy (=last day of RT)/ 6 months after end of RT.

-**EFS**=Event-free survival (time from beginning of RT to any failure or death from any cause, all patients). Follow-up over 2 years after end of RT.

-**PFS**=Progression-free survival (time from beginning of RT to progression of lymphoma or death from any cause, patients in PR or SD). Follow-up over 2 years after end of RT.

-**RFS**=Recurrence-free survival (time from beginning of RT to recurrence of lymphoma or death from any cause, patients in CR). Follow-up over 2 years after end of RT.

-**LSS**=Lymphoma-specific survival (time from beginning of RT to death related to lymphoma or associated with the treatment, all patients). Follow-up over 2 years after end of RT.

-**OS**=Overall survival (time from beginning of RT to death from any cause, all patients). Follow-up over 2 years after end of RT.

-Level of **cytokines IL-1 β , IL-4, IL-8, TNF α** and other inflammation relevant molecules: **Syndecan1 and MMP-2** and **S100 proteins** at baseline visit/ after 4 Gy/ after 10 Gy/ after 20 Gy on last day of RT/ at 3 and 6 months after end of RT.

-**Acute toxicities** during treatment, 6 weeks after end of RT, according to NCI-CTC

-**Chronic toxicities** from 3 months up to 2 years after end of RT, according to NCI-CTC/ LENT-SOMA.

-Incidence of **Adverse Events** (AEs) and **Serious Adverse Events** (SAEs), continuously.

4 Study Design

-Single-arm, prospective, open label, interventional, multicenter study.

-Historic data from irradiated patients with indolent gastrointestinal lymphomas serves as a basis for the intended response rate.

-Participation of further international sites with expertise in radiation treatment of gastrointestinal lymphomas after approval of their Ethics Committee/ IRB.

-Number of 79 patients need to be analyzed.

-Justification for 'single-arm design' and for 'non-inferiority limit': the low prevalence of the disease, the limited risk of the study design (because of the option of renewed RT in case of persisting disease) and the benefit in terms of lower risk of adverse reactions due to the lower RT dose of 20 Gy in comparison to standard dose of 30 Gy.

5 Study Sites and Study Population

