8.3.2 FU-2 – FU-6

The further exams take place quarterly in the first year after treatment (FU-2 – FU-5), afterwards an annual visit is scheduled (FU-6).

FU-2:	3 months after end of RT ± 3 weeks
FU-3:	6 months after end of RT ± 3 weeks
FU-4:	9 months after end of RT ± 3 weeks
FU-5:	12 months (1 year) after end of RT ± 3 weeks
FU-6:	24 months (2 years) after end of RT ± 3 weeks

The FU-2 and FU-3 visits include blood draw!

At all follow-up visits (FU-2 – FU-6) chronic radiogenic reactions must be documented (see Appendix 16.6 Adverse Reactions according to LENT SOMA).

Each follow-up visit consists of the following examinations:

- Anamnesis
- Clinical examination: ECOG, weight, blood pressure
(at FU-1/-2/-3/-5/-6)
- Quality of life assessment with QLQ-C30 and STO-22 (at FU-1/-2/-3)
- Endoscopy/ Endosonography (+ biopsies) (at FU-2/-3/-5/-6)
- CT-imaging (at FU-3/-5/-6)
- **Blood draw (at FU-2/-3):**
 - o –Routine: small blood count, LDH, GOT, GPT, alcalic phosphatase, γ-GT, bilirubin, creatinine.
 - o –**Research program (analyses at the University of Muenster!):**
Two 7.5 - 9 ml serum monovettes.
Centrifugation, freezing and storage see 3.1.3 and Appendix 16.7 (SOP BLOOD SAMPLES for RESEARCH PROGRAM)
Transmission of frozen blood samples to Radiobiology lab, Muenster at the cost of Dept. of Radiation Oncology, University Hospital Muenster
- Chronic radiogenic reactions must be documented (see Appendix 16.6 Adverse Reactions according to LENT SOMA)

The FU-6 is the study termination visit and ends the study regularly.

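### The stated end of data collection (28 February 2022) does not fit the 2-year follow-up defined for the secondary endpoints, and no later data cut is given

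*Protocol*

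**What the plan says.** Protocol 3.2.2 gives EFS, PFS, RFS, LSS and OS each the same horizon: "Follow-up over 2 years after end of RT". It collects chronic toxicity from 3 months to 2 years after RT. Section 8.3.2 puts FU-6 at 24 months, plus or minus 3 weeks, with endoscopy, CT and chronic reactions, and states: "The FU-6 is the study termination visit and ends the study regularly".

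The calendar in 10.1 is shorter:

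- "Planned start of data collection (first patient inclusion): September 01, 2019"
- "Planned recruitment duration: 1.5 years"
- "Last patient inclusion: February 28, 2021"
- "Planned overall duration of the study: 2 years"
- for the end of data collection, originally 31 August 2021: "the study period will be extended by 6 months until February 28 2022"

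The synopsis (1.3) repeats the February 2022 end date and plans the final report for 28 February 2023. It describes a patient's participation as "RT intervention of two weeks plus 6 months after end of treatment", whereas 10.1 gives 6 months to 2 years.

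Two other places bear on the point. The visit table in section 8 groups FU-4 to FU-6 under a post-trial follow-up heading. Section 8.4 asks for annual status reports after study termination.

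**The concern.** Eighteen months of recruitment plus 24 months of follow-up cannot fit into 30 calendar months. If the stated end of data collection is followed, many patients leave observation before the visit on which the 2-year endpoints depend.

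The 2-year relapse and late-toxicity results are the trial's evidence that a reduced dose holds up beyond the 6-month response. If they are incomplete because of the calendar, the report will describe a 2-year horizon that a large part of the cohort never reached.

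**Working it through.** **Inputs.** First inclusion is 1 September 2019, last inclusion 28 February 2021, and data collection ends on 28 February 2022 (10.1). RT lasts two weeks (1.3). RT starts 0 to 3 months after enrollment (section 6). FU-6 is at 24 months ± 3 weeks (8.3.2). Patients assigned: 83 (11.2). The accrual pattern is not given; even accrual over the 547 recruitment days is my assumption.

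**The plan's own figure.** 18 months of recruitment + 6 months to the primary endpoint = 24 months, which is the stated overall duration of 2 years. Adding 6 months gives 30 months, ending on 28 February 2022. The duration reproduces, but only as recruitment plus the primary follow-up.

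**Share reaching FU-6 by 28 February 2022.** Latest enrollment date = 28 February 2020 − 14 days of RT − wait before RT (+ 21 days if FU-6 is done at the early edge of its window). Share = days from 1 September 2019 to that date, inclusive, / 547.

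| Wait before RT | FU-6 timing | Latest enrollment | Share | Of 83 |
|---|---|---|---|---|
| none | nominal | 14 Feb 2020 | 167/547 = 30.5% | 25.3 |
| none | 3 weeks early | 6 Mar 2020 | 188/547 = 34.4% | 28.5 |
| 3 months | nominal | 15 Nov 2019 | 76/547 = 13.9% | 11.5 |
| 3 months | 3 weeks early | 6 Dec 2019 | 97/547 = 17.7% | 14.7 |

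A 1-month wait gives 25.0% at the nominal date and 28.9% at the early edge.

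**Follow-up time available to the survival endpoints.** Follow-up after RT is capped at 24 months. Events and drop-out are ignored, so this is the administrative maximum.

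- No wait: the last patient has 30 − 18 − 0.5 = 11.5 months. Those enrolled after month 5.5 average (24 + 11.5)/2 = 17.75 months. Overall mean = (5.5 × 24 + 12.5 × 17.75)/18 = 19.7 months, or 82% of 24.
- 3-month wait: the last patient has 8.5 months. Those enrolled after month 2.5 average (24 + 8.5)/2 = 16.25 months. Overall mean = (2.5 × 24 + 15.5 × 16.25)/18 = 17.3 months, or 72% of 24.

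**Primary endpoint.** A patient included on 28 February 2021 finishes RT between 14 March and 13 June 2021. FU-3 then falls between mid-September and mid-December 2021. Three more weeks for the window still leave it before 28 February 2022.

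**When the last FU-6 falls.** The nominal date is between mid-March and mid-June 2023, or early July 2023 with the late window. The nominal dates are about 12.5 to 15.5 months after the stated end of data collection, and later than the planned final report of 28 February 2023.

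**The case against.** The best defence is that the short calendar describes only the trial phase. The visit table separates baseline to FU-3 from FU-4 to FU-6. On that split, the synopsis figure of RT plus 6 months is the trial phase, and the longer range in 10.1 adds the follow-up. Annual status reports (8.4) show that later information is expected. This explains how the dates arose, so the two participation durations need not be a flat contradiction. It does not settle the matter. Section 8.3.2 places the regular end of study at FU-6, and 8.4 begins only after that with no scheduled examinations. Section 10.1 ends data collection without limiting this to one phase, and the report date in the synopsis is exactly 12 months after that end.

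A reader might infer three stronger things that the documents do not support:

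- **That only the earliest enrollees inform the survival endpoints.** The synopsis plans a one-sample log-rank test for time-to-event endpoints, and patients censored before 24 months contribute to it. The shares above count patients who reach FU-6; they do not measure the information available for EFS or OS.
- **That about a third is an upper bound.** It holds under even accrual; faster early recruitment would raise it.
- **That the primary endpoint is at risk because the extension also prolongs recruitment.** Section 10.1 keeps last inclusion at 28 February 2021.

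It can also be said that data cuts are commonly left to a statistical analysis plan. That is fair for the timing of analyses. Here, however, the protocol itself fixes the endpoint horizon, the termination visit and the end of data collection, and they disagree.

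**Conclusion.** The conflict stands. Followed as written, the dates let roughly 14% to 34% of patients reach FU-6, assuming even accrual and a wait before RT of 0 to 3 months. The main loss is 2-year toxicity, the 24-month endoscopy and CT, and precision in the later part of the survival curves. The survival analyses remain possible with censoring, on about 72% to 82% of the planned follow-up time.

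The 6-month response analysis is untouched at the stated last-inclusion date. Section 11.3 treats all analyses beyond the primary as exploratory, so the sample size, error rate and non-inferiority conclusion do not depend on this. It should be fixed, but it does not undermine the trial's main result.

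**What to change.** Amend the protocol as follows:

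1. State that the 28 February 2022 cut applies to the primary analysis, once the last patient has had FU-3.
2. Set a second cut for the survival and late-toxicity endpoints when the last patient has reached FU-6: mid-March to early July 2023 for last inclusion on 28 February 2021.
3. Move the end of data collection and the report of the secondary endpoints to match the second cut.
4. Use one participation duration in 1.3 and 10.1, and reconcile the post-trial label in the visit table with the role of FU-6 in 8.3.2.

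Shortening the endpoints to 1 year while keeping the February 2022 cut would not solve the problem. A patient included on 28 February 2021 who starts RT at once nominally reaches 12 months in mid-March 2022. With a 3-month wait for everyone, only 14.5/18 = 81% reach 12 months by the cut under even accrual.

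The visits are already scheduled, so the change is to dates and labels. The price is continued data collection and a later report of the secondary endpoints.

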11.1 Methods against bias

Deviating radiation doses or field sizes and differences in expertise of persons executing radiation treatment are potential sources of bias. All patients fulfilling the inclusion and no exclusion criteria and providing informed consent will get the single-arm radiation concept with 20 Gy with clear directives for Investigational project/ Medical procedure. Moreover, the participating sites are limited to university centers and large radiooncological centers, some of them already showed good recruitment in the previous studies, for ensuring a high consistent level of expertise. Because of the low incidence of the disease and the limited trial period a one-sample design is chosen for this study, a randomized trial is biometrically not possible. As there is only one arm no blinding takes place.

11.2 Proposed sample size/Power calculations

The primary endpoint ORR 6 months after the end of RT will be analyzed by a one-sample binomial test. Based on previous studies (Tsang 2003, Teckie 2015) the OR rate of the standard 30 Gy treatment is assumed to be 95%. The same OR rate is assumed for the interventional 20 Gy treatment. To show the non-inferiority of the interventional treatment to a non-inferiority margin of 10% (i.e. show that the ORR is greater than 85%) with 80% power and one-sided significance level 2.5% a number of 79 patients need to be analyzed. It is assumed that 95% of patients assessed for eligibility are assigned to the trial from which another 95% of patients can be analyzed (drop-out rate 5%). That is the needed number of patients to be assigned to the trial is 83 and the necessary number of patients assessed for eligibility is 88.

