Inclusion Criteria:	
 -primary indolent gastric or duodenal lymphoma -pathology: marginal zone lymphoma (MZL) or follicular lymphoma (FL) -stage: clinical stage I or II (Ann Arbor classification) -H. pylori negative or antibiotic resistant lymphoma -any FLIPI score low – high (0-4) -any size of tumor or affected lymph nodes -male or female with age \geq 18 years -performance status ECOG 0 – 3 -written informed consent by the patient
Exclusion Criteria:	
 -prior radiation treatment of the gastrointestinal lymphoma -stage: clinical stage III or IV (Ann Arbor classification)-inability to understand the informed consent or unwillingness to participate in the study -severe comorbidity or organ dysfunction contraindicating the use of RT (liver cirrhosis Child-Pugh C, chronic obstructive pulmonary disease GOLD 4, heart insufficiency NYHA IV, dialysis dependent renal insufficiency, uncontrolled epilepsy) -known seropositivity for HIV -acute hepatitis B or C infection -chronic inflammatory bowel disease -prior malignant disease (exclusion: basalioma, non-metastasized solid tumor in constant remission diagnosed >3 years ago) -pregnancy or breastfeeding -active substance abuse or severely compromised compliance
Statistical Methods:	
Primary endpoint analysis:
 
The primary endpoint is the overall response rate (ORR) 6 months after end of treatment. It will be analysed by a one-sample non-inferiority binomial test. The one-sided significance level is 2.5%, the power is 80%.
 
It will be tested whether ORR will be non-inferior to 0.95, with non-inferiority margin (difference) 0.1, i.e. it will be tested whether the lower limit of the one-sided 97.5% confidence interval by Clopper-Pearson will be greater than 0.85.
 
Secondary endpoint analysis:
 
The pre-specified secondary endpoints will be analysed with appropriate statistical methods depending on the type of variable, e.g. rates are analysed by binomial test and exact 95%-confidence interval, time-to-event endpoints by one-sample log-rank test.

Number of Patients/ Sample size:	
To be assessed for eligibility: n = 88
 
To be assigned to the trial: n = 83
 
To be analyzed: n = 79

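### The 79/83/88 chain rounds 83.16 down to 83, and under the plan's exact test the stated 80% power becomes 76.5% if ITT means that all 83 assigned patients are analysed (minor)

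*Protocol*

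**What the plan says.** Section 11.2 sizes the trial on a response rate of 95% for 30 Gy, the same rate for 20 Gy ("The same OR rate is assumed for the interventional 20 Gy treatment") and a margin of 10 points, so the limit to exclude is 85%. It states that "with 80% power and one-sided significance level 2.5% a number of 79 patients need to be analyzed". It then assumes that 95% of those assessed are assigned and that 95% of those assigned can be analysed, and concludes that "the needed number of patients to be assigned to the trial is 83 and the necessary number of patients assessed for eligibility is 88".

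The synopsis repeats the counts ("To be assigned to the trial: n = 83") and makes the success criterion exact: the test is whether "the lower limit of the one-sided 97.5% confidence interval by Clopper-Pearson will be greater than 0.85". Section 11.2 names the test ("The primary endpoint ORR 6 months after the end of RT will be analyzed by a one-sample binomial test") but not the formula that produced 79.

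Section 11.3 defines the primary analysis set in two ways in one sentence: as the patients who are to be analysed, and as following the ITT principle. The synopsis attaches the first label to 79. The second would ordinarily mean everyone assigned, which is 83.

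**The concern.** A required minimum is rounded up. Here the step from 79 to 83 is rounded down, while the next step, from 83 to 88, is rounded up. Taken alone this is a one-patient slip.

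It deserves a note because the criterion is an exact binomial one, and exact power does not rise smoothly with the number of patients. It falls slowly while the permitted number of non-responders stays fixed, then jumps when one more is permitted. The printed 83 is the last count before such a jump. If the primary analysis includes all assigned patients, the stated 80% does not hold at the stated number.

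**Working it through.** **Inputs** (section 11.2 and synopsis): null rate 0.85, assumed rate 0.95, one-sided alpha 0.025, power 0.80, 95% of assessed patients assigned, 95% of assigned patients analysed, Clopper-Pearson lower limit above 0.85.

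**1. Reproducing 79.** The one-sample normal approximation with null and alternative variances is

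n = [(1.96·√(0.85·0.15) + 0.8416·√(0.95·0.05)) / 0.10]² = 78.02, rounded up to 79.

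Other common variants miss: alternative variance only 37.3, null variance only 100.1, arcsine 66.2, continuity-corrected 87.7. That 79 came from this approximation is an inference, because the protocol names no formula.

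**2. The drop-out chain.**
- 79/0.95 = 83.16. Rounded up this is 84; the protocol prints 83.
- 83/0.95 = 87.37, rounded up to the printed 88. From 84: 84/0.95 = 88.42, rounded up to 89.
- Forwards: 83 × 0.95 = 78.85 analysable, which is 0.15 short of 79. From the start of the chain, 88 × 0.95 × 0.95 = 79.42.

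Rounded up throughout, the chain is 79/84/89.

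**3. Exact test.** For each n, take the smallest r with P(X ≥ r | n, 0.85) ≤ 0.025. This is the same as a Clopper-Pearson lower limit above 0.85. Power is P(X ≥ r | n, 0.95).

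| n | responders needed | lower limit at r | exact alpha | power at 95% |
|---|---|---|---|---|
| 75 | 70 | 0.851 | 2.3% | 82.8% |
| 79 | 74 | 0.858 | 1.6% | 79.7% |
| 83 | 78 | 0.865 | 1.0% | 76.5% |
| 84 | 78 | 0.851 | 2.4% | 87.3% |

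At n = 83, 77 responders give a lower limit of 0.8493 and just fail. So 83 and 84 patients need the same 78 responders, and 84 allows one more non-responder.

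**4. Three readings of the primary analysis set.**
- *All assigned analysed, with response status known for all:* 76.5% at 83 and 87.3% at 84. If one of the 84 is lost, the count is 83 again and power returns to 76.5%.
- *Completers only, each assigned patient analysable with probability 0.95:* averaging exact power over the number analysed gives 79.5% with 83 assigned and 79.1% with 84.
- *All assigned analysed, drop-outs counted as non-responders (an assumption; the protocol does not say so):* the effective response rate is 0.95 × 0.95 = 0.9025, and power is 16.9% at 83 and 27.8% at 84.

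**The case against.** The strongest reply is that nothing of substance is lost. The shortfall is 0.15 patient under round planning assumptions, 88 assessed does yield 79 analysable on average, and exact power at 79 is 79.7%, which rounds to the stated figure. If drop-outs are removed, as section 11.2 plans, an 84th patient adds nothing on average. All of this stands, and it is why the point is minor.

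Three stronger readings are tempting and are not supported.

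- A reader might compute that 83 assigned patients leave fewer than 79 analysable about 40% of the time and call the target unreliable. Of that 40.1%, 37.8 points fall on 75 to 78 patients, where exact power runs from 82.8% down to 80.5%, all above the 79.7% at 79. Only 2.3 points fall below 75. Missing 79 by a few is mostly harmless.
- A reader might conclude that one more patient buys 10.8 points of power (87.3% − 76.5%). That holds only if exactly 84 are analysed. Nor is 83 the weakest count overall: it is the bottom of one step, and n = 74 gives 68.9%.
- A reader might take 83 to be the established denominator. Section 11.3 also refers to the patients to be analysed, the label the synopsis gives to 79, so the all-assigned reading is permitted but not settled.

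What the reply does not remove is that the ITT wording permits a denominator of 83, and at 83 the stated power and the stated criterion disagree.

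**Conclusion.** The point holds as a minor one. The assigned and assessed counts are each one below what the plan's own 95% rules give when rounded up throughout (84 and 89 instead of 83 and 88). The rounding itself is immaterial. The planned 79 is sound under the exact test, at 79.7%.

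The one material consequence depends on section 11.3. If ITT means all 83 assigned patients, power is 76.5%, which is 3.5 points below the stated 80%, with exact alpha of 1.0%. This assumes a true response rate of 95% and no drop-out counted as a non-responder. If drop-outs do count as non-responders, power is far below 80% at either number (16.9% and 27.8%). That follows from how the denominator is defined, not from the rounding, and going to 84 does not repair it.

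The documents do not show that the trial is invalid or that 79 is the wrong target.

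**What to change.** In section 11.2 and the synopsis, either restate the chain as 79 analysed, 84 assigned and 89 assessed, or keep 83 and 88 and restate the power.

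In either case, say which set the primary analysis will use and give exact-test power for it: 79.7% at 79 (74 responders needed), 76.5% at 83 (78 needed), 87.3% at 84 (78 needed). Add that the figure for 84 holds only if all 84 are analysed. If drop-outs are to count as non-responders, give the power for that case as well.

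Do not write that 79 was derived from the exact test, since it matches the normal approximation. It is enough to report the exact power that 79 provides.

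The cost is wording in two places and at most one more assigned and one more assessed patient.
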